2.3 Interest for children

So far, research around COVID 19 tends to focus on disease evolution and treatment in the adult population. This is based on the observed incidence, disease severity and the high mortality in the adult population, with either intense exposure (health care professionals) or high risk factors for critical disease such as older age, diabetes, cardiovascular disease, hypertension, chronic respiratory disease, immune compromised disease and obesity. In younger adults, obesity seems to be the major risk factor for critical illness. Children seem less often affected or develop more often the asymptomatic, aspecific and mild variant of the COVID-19 disease. However, more recent observations demonstrate that not all children escape critical illness and even more important, that the critical illness may or may not be caused by the same pulmonary symptomatology. In Madrid, 60% of the 41 children with confirmed COVID-19 during the first two weeks of the epidemic were hospitalised, and 9,7% of them had to be admitted to the paediatric intensive care unit . More recent observations suggest that the virus may be involved in the Pediatric Inflammatory Multisystem Syndrome- a new clinical entity characterized by multiple organ inflammation accompanied in some cases by organ failure and up to 40-50% of cases by choc.

In Luxembourg, two previously healthy children (<12 years) have suffered from severe cardiac involvement (myocarditis and Kawasaki disease) induced by the COVID-19, requesting intensive care treatment, based on their clinical condition (personal observation) (retrospective diagnosis of PIMS). Whether rare immune mechanisms (IEI - inborn errors of immunity, host genetic susceptibility in innate immunity -related genes) or environmental factors are involved in these cases is unknown.

Risk factors for severe disease in children need to be elucidated. This would allow not only better understanding of the pathophysiology and dynamics of COVID-19 in children, but also the development of relevant public health measures in order to optimize protection for those children who are vulnerable (ex by vaccination when available in the future).

This pediatric extension of the study aims to identify factors associated with the COVID-19 disease severity (or lack of it) in children with an in-depth characterization of the clinical, biological and microbiological characteristics of COVID-19 in children.

Stools sample have been planned at each study visit in the children sample strategy, both for Covid-19 positive and household contact children, to increase the understanding of virus shedding in stool and the influence of the microbiota on Covid-19 infection in the children population.

2.4 Long-term consequences of Covid-19

Given the current body of knowledge, **there are key unsolved questions around the long-term (beyond 3 weeks) health consequences of Covid-19**, which in the absence of any consensus has been termed as “Long Covid” or “Long Haulers” in recent publications[14]. Also named **Chronic Covid Syndrome (CCS)**, this condition needs to be better described and understood. So far, it has been shown that a fraction of the Covid-19 patients who undergo a variable acute symptomatic phase of the disease are coming forward with continuing effects of the disease, with complaints such as mental fog, delayed latent periods in recalling events of recent past, tachycardia, extreme fatigue, inability to perform daily physical tasks[15]. The signs and symptoms are so diverse and related to multiorgan and systems that it is challenging to ascribe it a proper terminology[16]. It has also been recognized that there are Covid-19 affected patients in which renal, cardiac, neural, gastrointestinal, and coagulative features

dominate and threaten the life of the patients[17]. That being said, the majority of the data come from hospitalized patients and few studies report long-term health consequences of asymptomatic or mildly symptomatic forms of Covid-19. However it has been shown that a vast majority of patients with home based recovery had frequent cardiac inflammatory involvement, which was similar to the hospitalised subgroup with regards to severity and extent[18]. A call for more research has been recently released by doctors in the BMJ[19].

Only some of the above-mentioned long-term health related consequences of Covid-19 are covered in the monthly questionnaire in Predi-COVID. The last monthly questionnaire at the end of the follow-up (month 12) has been more detailed, to collect complementary information on a large spectrum of chronic conditions or symptoms potentially related to Covid-19 to increase the value of the Predi-COVID cohort study and associated spin-off projects.

To align with new research questions around Long Covid and its long term presentation, the total follow-up duration for participants has been extended to 2 years, with Long-Covid specific questionnaires at months 15 and 24 for all participants and a new biological sampling at 15 and 24 months.

2.5 Reinfection and infection post-vaccination

The vaccination campaign has picked up speed all over the world but coverage is still not yet sufficient in Luxembourg, as in many countries. Open questions begging to be answered and future risks remain (variants of concern, new waves, vaccination escape, immune response dynamic, reinfections, infections before and after vaccination). In this perspective there is a need for more information on infections post-vaccination but also on reinfections. These results will help to guide the national authorities to adapt its crisis management strategy.

In particular, the short- to mid- term impact of vaccination in relation to the evolution of immunity and breakthrough infections by variants, and how this knowledge could be used to inform the future vaccination strategy in Luxembourg is of high interest.

2.6 Health economics

The impact of the Covid-19 pandemic on the health system, at both the individual and population level is still understudied. Questions related to work ability and long-term care costs remain unanswered questions. By linking data from Predi-COVID with medico-administrative data from the IGSS (Inspection Générale de la Sécurité Sociale), we will have the opportunity to 1) better describe the overall healthcare pathway of individuals with Covid-19 before and after the infection, both in terms of healthcare consumption and costs and 2) assess the impact on the socioeconomic and work environment in Luxembourg.

2.7 Risk/benefits assessment

The risks associated with this study protocol in the population described above are described below:

| Procedure – type of sample | Associated risk |
|-----------------------------------|--|
| Blood sample | Pain, bruising, tiredness or fainting, infection |
| Nasopharyngeal swab | Discomfort during brushing, bleeding, infection |
| Oropharyngeal swab | Discomfort during brushing, bleeding, infection |
| Stool collection | No known risk, infection to person handling sample |
| Sputum/saliva collection | No known risk, infection to person handling sample |
| Usage of smartphone app | Minimal associated risks * linked to the use of a healthcare application on a mobile phone |
| Hair sample | No known risk, infection to person handling sample |

*There are some risks linked to the fact that the study is conducted exclusively online (hacking of the participating account, risk of jeopardizing the confidentiality of health data and other personal data). All precautions will be taken for the patients, the family members and nurses during samples and data collection, according to the rules in force at the time of the study.

The benefit for the participant will be to benefit from an additional tool allowing a daily monitoring of their health status and to participate in an innovative research project in the current crisis context and to contribute to the common effort in the fight against the COVID-19 pandemic.

3. OBJECTIVES

3.1 Principal objective

The main objective of Predi-COVID is to identify clinical, epidemiological and omics characteristics associated with the severity of COVID-19, which will then be used to further stratify the study population into clusters of disease severity with similar patterns and disease courses.

3.2 Secondary objectives

Secondary objectives include

- to study the long term (up to 2 Year) health consequences of COVID-19.
- to characterise clinical symptoms and biological markers for individuals with re-infection/infection post-vaccination and Long COVID
- to describe the trajectories of symptoms after being positively diagnosed to COVID-19
- to identify vocal biomarkers associated with respiratory syndromes, fatigue, anxiety or emotions related to COVID-19 which could then further be used for easy remote monitoring of COVID-19 patients.
- to identify the virological factors and the individual characteristics involved in viral escape to COVID-19 vaccines and in reinfections
- to characterize the cellular and antibody responses (type and durability) elicited by vaccines and in uninfected and recovered COVID-19 patients (either vaccinated or not) with an emphasis on the variability of immune responses

4. EVALUATION CRITERIA

4.1 Main Evaluation Criteria

- **Hospitalization** : Hospitalisation and Duration of hospitalization (days)
- **Intensive care** : intensive care / resuscitation and duration of intensive care / resuscitation
- **Ventilation** : ventilation and duration of ventilation
- **Transfert to a hospital outside Luxembourg**
- **Clinical severity**
- **Death**

4.2 Secondary Evaluation Criteria

Analytical endpoints to be evaluated on the sub-cohort with complete data

- **Quantitative**
 - o The charlson index
 - o Whole blood count parameters

- Plasma cytokine levels
- Peripheral cell immune phenotyping
- TCR repertoire of CD4 and CD8 T cells
- IgG and IgM titers
- hormones/glucocorticoid concentration
- **Qualitative**
 - Syndromic respiratory disease panel results
 - COVID-19 mutations
 - HLA genotypes

Criteria may be modified as we acquire knowledge on the infection. Updates of these criteria will be made as needed.

5. STUDY DESIGN

[figure not shown]

Figure 1. Overview of Predi-COVID design and data collection.

Predi-COVID is a prospective cohort study composed of people positively tested for COVID-19 in Luxembourg, followed with a remote system for monitoring participants' health evolution and symptoms. After explicit consent, virtually all adults ≥ 18 years and all children < 18 years with confirmed COVID-19 infection (positive by RTqPCR test) could be included in the Predi-COVID cohort.

A sub-sample of a minimum 320 adults and 100 children will be included in the deep-phenotyping sub-study. This number will be adapted to quickly evolving knowledge on COVID-19 and to the resources available to include and sample patients.

For hospitalized patients, the protocol encompasses a face-to-face inclusion combined with daily evaluations up to death or discharge (using ISARIC modified CRF (CORE + DAILY modules)). From discharge, participants will then be asked to enter the "Home" protocol. At home, a digital follow-up thanks to a remote system (web or mobile app) and the CoLive LIH smartphone app will be performed for both health status and symptoms checks as well as for research-oriented data collection.

Adult and child participants in Predi-COVID will be actively followed for 14 days from the time of confirmation of diagnosis, whether they are at the hospital or at home in isolation or quarantine. Short evaluations will be also performed at week 3 and week 4 and then monthly for a period up to 12 months to assess potential long term consequences of COVID-19.

A biological sampling is performed at baseline and at 6 months for all Predi-COVID participants.

6. STUDY POPULATION

The Predi-COVID cohort will be composed of volunteered Covid-19 positive patients identified in the centralized database of all diagnostics tests performed in Luxembourg, managed at the Health Directorate.

A sub-sample will be invited to perform complementary clinical data and biological samples collection. Therefore, the study will collect data on all cases and comprise more detailed data and associated samples for a minimum of

200 adult participants and 100 children. The basic sampling scheme for participants will consist in 2 sampling visits, one at baseline and one at 6 months.

In addition, adults presenting a reinfection or a post-vaccination infection will be invited to do 2 specific sampling visits at 3 weeks and 2 months to answer specific research questions on vaccination and reinfections.

6.1 Inclusion criteria

For the **Predi-COVID** cohort, in order to be eligible to participate in this study, an individual must meet all the following criteria:

- Signed informed consent form by the patient (adult) and caregiver/parent (child)
- Adult (≥ 18 years old), child and adolescent (0-17 years old) patients with *confirmed SARS-CoV-2 infection as determined by PCR, performed by one of the certified laboratories in Luxembourg*
- Hospitalized or at home

6.2 Exclusion criteria

An individual who meets any of the following criteria will be excluded from participation in this study:

- *Patients not able to understand French or German*

6.3 Screen Failures

False positive diagnosis

6.4 Strategies for recruitment and retention

All positive patients (or his/her legal representative) will be contacted by phone by collaborators from Sanitary Inspection and asked if they consent to the communication of their contact details to the LIH with regard to a possible participation in a research project on Covid-19. The cohort will be constituted by virtually all volunteered positive Covid-19 cases detected in Luxembourg and will include a subsample of 200 adult and 100 child patients with visits at home for additional biosampling for research.

People who did agree will be contacted by phone by an experienced nurse or clinical research associate from the CIEC who will explain the study and organize the visits at home or at hospital. The informed consent process is detailed in chapter 14.1. The CIEC team of LIH will be in charge of the follow-up of the participants and of the organization of the visits.

7. Biological samples and data collection

7.1 Data collection and sample collection (for the sub-sample only)

The samples and data collected during the study course are described in the table below. The participants will be able to participate either in data collection only or in both data and sample collection. For sample collection they can choose to do all or part of the sampling.

| Predi-COVID | | | | | | | | |
|---|--|---|--|------------------|--|------------------|-----------------------------------|-----------------------------------|
| | Screening | Inclusion | Baseline visit | Visit (3 weeks)* | Visit (2 months)* | Visit (6 months) | Visit (15 months) | Visit (24 months) |
| Eligibility assessment | x | | | | | | | |
| Informed consent | x (oral consent to be contacted by LIH) | x (e-consent for data collection) | X Written consent for sample collection, scanned on site and stored electronically at LIH | | | | | |
| Clinical data (ISARIC protocol CRF data) | | x Daily data collection for up to 30 days for hospitalized patients or once at baseline for patients at home | | | | | | |
| Online questionnaires (for adult participants and children >10 years) | | Daily data collection for 14 days and weekly at weeks 3 and 4 | | | Monthly follow up (1 to 11 months after inclusion), detailed questionnaire Long Covid at M12 | | Detailed questionnaire long covid | Detailed questionnaire long covid |

| | | | | | | | | |
|---|--|---|---|---|---|---|---|---|
| CoLive LIH smartphone application (optional, for adults and children >10 years) | | Regular voice recordings + short questionnaires | | | | | | |
| Blood sample : up to 50mL (for children, volume adapted to child's weight) | | | x | x | x | x | x | x |
| Stool sample | | | x | | | x | x | x |
| Induced sputum or saliva | | | x | | | x | x | x |
| Nasopharyngeal swab | | | x | x | | x | x | x |
| Oropharyngeal swab | | | x | | | x | x | x |
| Hair sample | | | x | | | x | x | x |

- only for ADULTS, with a re-infection or an infection post-vaccination

[1] See « Annexe 2 de l'arrêté du 17 février 2021 fixant la liste des recherches mentionnées au 2° de l'article L. 1121-1 du code de la santé publique » - https://www.legifrance.gouv.fr/loda/article_lc/LEGIARTI000033546109/2016-12-07/

7.2 Predi-COVID biological characterization (according to sample type) (not exhaustive)

- Blood sample :
 - Blood Count
 - CRP

- HLA genotype
 - **Antibodies to SARS CoV2**
 - Antibodies to CoV OC43, NL63 and 229E (optional)
 - Immunophenotyping
 - TRC repertoire
- Swabs :
 - SARS-CoV-2 and other CoV specific RT-PCR
 - Molecular diagnosis for rhinovirus, adenovirus, picornavirus, RSV, influenza A and B, parainfluenza 1-3, human metapneumovirus, *M. pneumoniae*, *C. pneumoniae*, *L. pneumophila*
 - Sequencing of viral PCR targets for confirmation and identification of mutations
 - Sputum/saliva :
 - cell number, eosinophilic cationic protein, IL8, fibrinogen (optional)
 - Hair :
 - hormones/glucocorticoid concentration
 - Stool :
 - SARS-CoV-2 and other CoV specific RT-PCR
 - virus isolation, sequencing and characterization (optional)
 - microbiome-omics

7.3 Ancillary study: Predi-COVID-H

The samples and data collected during the study course are described in the table below. The Predi-COVID-H participants will be able to participate either to data collection only or to both data and sample collection. For sample collection they can choose to do all or part of the sampling. Since the national recommendations for the follow-up of contact persons of positive cases have recently changed with the prescription of a PCR test 5 days after the test of the case person, we adapted our sampling strategy with a follow-up visit conditioned by the PCR test result.

| Predi-COVID-H | | | |
|--|---|--|--|
| | Inclusion | Follow-up | |
| | | If RTqPCR prescribed by Sanitary Inspection results = negative | If RTqPCR prescribed by Sanitary Inspection results = positive |
| Informed consent | X (e-consent for data collection and written consent for sample collection, but stored electronically) | | |
| Data collection : online questionnaires (for adult participants and children > 10 years) | | Data collection daily for up to 14 days | |
| CoLive LIH application (optional, for adults and children >10 years) | | Regular voice recordings + short questionnaires | |

| | | | |
|--|---|--------------|--|
| Blood sample : up to 50mL (for children, volume adapted to child's weight) | X | X (6 months) | |
| Nasopharyngeal swab | x | x (6 months) | |
| Oropharyngeal swab | x | x (6 months) | |
| Stools | x | x (6 months) | |
| Hair sample | x | x (6 months) | |
| Sputum/saliva | x | x (6 months) | |
| End of study | | | X (contacts with positive PCR will be proposed to be enrolled in the Predi-COVID cohort and to start the follow-up at inclusion visit Predi-COVID) |

➤ **Predi-COVID-H biological characterization (according to sample type) (not exhaustive)**

Blood sample :

- **Antibodies to SARS CoV2**
- Immunophenotyping
- TRC repertoire
- Antibodies to CoV OC43, NL63 and 229E (optional)

Stool :

- SARS-CoV-2 and other CoV specific RT-PCR
- Microbiome-omics

Sputum/saliva :

- cell number, eosinophilic cationic protein, IL8, fibrinogen (optional)

Hair :

- hormones/glucocorticoid concentration

Swabs :

- SARS-CoV-2 and other CoV specific RT-PCR
- Molecular diagnosis for rhinovirus, adenovirus, picornavirus, RSV, influenza A and B, parainfluenza 1-3, human metapneumovirus, *M. pneumoniae*, *C. pneumoniae*, *L. pneumophila*
- Sequencing of viral PCR targets for confirmation and identification of mutations

[figure not shown]

Figure 2 - Summary of the sample strategy in the subsample cohort.

8. PARTICIPANT DISCONTINUATION/WITHDRAWAL

Participant Discontinuation/Withdrawal from the Study

Patients can leave the study at any time for any reason if they wish to do so without any consequences. In this case, the data and samples already used for the study cannot be destroyed.

The subjects enrolled in the study in the Predi-COVID-H cohort (living with positively tested subjects) will be discontinued after 1 week if they returned seronegative results AND are symptom free one week after the inclusion in the study.

Lost to Follow-Up

Participants will receive questionnaires during the 12 months of the study except if they explicitly ask not to be contacted any more. Lost to follow-up participants are those who will not answer any of the questionnaires after baseline.

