| 
Ancillary study
 | 
An ancillary study will be added (Predi-COVID-H). For patients included as well as subjects living with positively tested patients on the basis of a volunteer informed consent.
 
Predi-COVID-H is an ancillary cohort study composed of Household members of index cases to monitor symptoms and disease outbreak in this high-risk population. For every asymptomatic member of the family of a “case” included in the Predi-COVID sub-sample (a “contact”), clinical as well as socio-economic characteristics will be collected. Biological samples will also be collected at the same time as the “case” visit by nurses and up to 50 ml of blood, nasopharygeal and oropharyngeal swabs, stool, saliva and hair samples will be taken at baseline for adults and children. According to the new recommendations of the Health Directorate, all Household contacts of positive cases are invited by the Sanitary Inspection to be tested 5 days after the diagnostic test of the “index case”. In case of positive result, the “contact” will be proposed to be enrolled in the Predi-COVID study. Otherwise, a second visit will be planned 6 months later, to collect blood, nasopharygeal and oropharyngeal swabs, stool, saliva and hair samples. All “contacts” will be followed digitally.
 
Predi-COVID-H inclusion criteria:
 
 ● Adult and children (0-17 ans) house members of COVID-19 positive participants. 
Exclusions criteria :
 
 ● Patients not understanding French or German 
Sample size: A minimum of 100 participants (adults and children) will be included in the sub-study on house-members. The sample size and the sampling strategy may have to be adapted to the rapidly evolving knowledge on COVID-19.
 |
|-------------------------------|--|

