11.4 Statistical analyses

Descriptive statistics will be produced for the main endpoints, namely hospitalisation, intensive care / resuscitation admission, ventilation, their duration, death and severity of the disease. Secondary endpoints together with other variables including potential prognostic factors of the disease will also be described with mean (+- STD) or frequencies (%) as adequate.

A logistic model will be used to study whether the risks of hospitalisation, intensive care admission or intubation as well as death are associated with a specific risk factor. adjustment will be done on age, gender and other potential confounding factors.

Factors triggering the severity of the disease will be evaluated with a Mantel-Haenszel chi square to evaluate if different levels of patients' characteristics are associated with a more serious form of the disease.

Further stratification of the patient cohort will be performed through Machine learning techniques to include biological and other omics measurements. A deep phenotyping related to the symptoms of the disease as well as biosampling allowing for laboratory-based and computational analytics will be performed. The stratification approach will include data-driven tools and allow to define disease trajectories that will be translated into clinical and/or biomarker-defined subgroups

The time to conversion from the PREDI-COVID-H cohort to the PRECOVID cohort will also be studied.

[figure not shown]
Missing data will not be replaced concerning the endpoints. A replacement method such as multiple imputations through chained equations will be envisaged for the other variables and risk factors.

The limits of the study linked to the size of the sample enrolled, the extent of the effects or the selection of participants and other potential limits will be evaluated and discussed.

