ANNEX 5 :

QUESTIONNAIRE PREDI-COVID-H

Utilisation du module e-PRO de Ennov Clinical

Questionnaires français

V1.0

Suivi à distance depuis un smartphone, tablette ou ordinateur :

- 1 questionnaire court par jour tant qu'il n'y a pas eu de confirmation de Covid19 par test positif et pendant 14 jours

Table des matières

[Système d'alerte](#)

[Questionnaire quotidien](#)

[Questionnaire permanent](#)

[Profil](#)

Questionnaire quotidien

Mon état de santé général

Vous êtes un membre du foyer d'une personne diagnostiqué positif à Covid19. Veuillez remplir ce questionnaire de suivi quotidien.

1) Date du questionnaire :

2) Avez-vous été testé et diagnostiqué positif à Covid19 ? Oui/Non

3) Vous êtes: A la maison / A l'hôpital / Autre

Si A l'hôpital : Lequel : menu déroulant

Centre Hospitalier de Luxembourg / Fondation Hôpitaux Robert Schuman / Centre Hospitalier Emile Mayrisch / Centre Hospitalier du Nord / Autre

4) Comment vous sentez-vous aujourd'hui ? Je me sens bien / Je me sens fatigué(e) / Je me sens mal

5) Avez-vous bien dormi ? Oui/Non

Si non, pourquoi ? [Champ libre]

6) Avez-vous une toux sèche ? Oui/Non

7) Avez-vous une augmentation de votre toux habituelle ces derniers jours ? Oui/Non

8) Avez-vous un mal de gorge apparu ces derniers jours ? Oui/Non

9) Avez-vous noté une forte diminution ou perte de votre goût ou de votre odorat ? Oui/Non

10) Avez-vous de la diarrhée ? Avec au moins 3 selles liquides/molles par jour. Oui/Non

11) Avez-vous des douleurs musculaires ou des courbatures inhabituelles ces derniers jours ? Oui/Non

12) Avez-vous des douleurs thoraciques ces derniers jours ? Oui/Non

13) Quel est votre niveau de douleur actuel ? (Notez de 1 à 10)

14) Avez-vous de la fièvre ? Oui/Non

Avez-vous un thermomètre ? Oui/ Non

Si oui, Veuillez prendre votre température :

15) Avez-vous des difficultés respiratoires ? Oui/Non

16) Avez-vous vu apparaître une gêne respiratoire ou une augmentation de votre gêne respiratoire habituelle ? Oui/Non

17) Quel est votre poids ? (se peser sans chaussure) __ kg ou Je ne sais pas

18) Avez-vous des difficultés importantes pour vous alimenter ou boire ? Oui/Non

19) Avez-vous d'autres symptômes ? Oui/Non

Si oui, veuillez préciser lesquels : [champ libre]

Questionnaire permanent

A ne remplir qu'une fois

Profil

-
- Sexe
- Date de naissance
- Poids (kg)
- Avant le diagnostic de Covid19, avez-vous perdu, sans le vouloir, 3 kg ou plus dans les 6 derniers mois ? (Oui/non)
- Taille (cm)

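### Section 8 ends household-contact follow-up at one week on serology and symptoms, while the synopsis, 7.3 and Annex 5 keep contacts without a positive PCR for 14 days of questionnaires and a 6-month visit

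*Protocol*

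**What the plan says.** Section 8 of the protocol states that household contacts in Predi-COVID-H "will be discontinued after 1 week if they returned seronegative results AND are symptom free one week after the inclusion in the study".

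The other places that describe follow-up of these contacts use a different criterion and a longer period:

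- **Section 7.3, introduction.** After a change in national testing recommendations, "we adapted our sampling strategy with a follow-up visit conditioned by the PCR test result".
- **Section 7.3, schedule table.** The questionnaire row reads "Data collection daily for up to 14 days". The PCR-negative column has blood, both swabs, stool, hair and sputum/saliva at 6 months. A positive PCR ends the ancillary study, and the contact is offered enrolment in Predi-COVID.
- **Synopsis, ancillary study.** A contact who tests positive is offered Predi-COVID. "Otherwise, a second visit will be planned 6 months later, to collect blood" and the other samples. All contacts are to be followed digitally.
- **Annex 5.** "1 questionnaire court par jour tant qu'il n'y a pas eu de confirmation de Covid19 par test positif et pendant 14 jours", that is, one short questionnaire a day for 14 days while no positive test has occurred.
- **Section 11.4.** "The time to conversion from the PREDI-COVID-H cohort to the PRECOVID cohort will also be studied".

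**The concern.** Study staff cannot follow both rules. A contact who is PCR-negative, seronegative and well at one week is out of the study under section 8, but is due for further questionnaires and a 6-month visit under the synopsis, 7.3 and Annex 5. No passage exempts such contacts from the later procedures, and none limits the 6-month visit to contacts with antibodies or symptoms.

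The synopsis says the household cohort exists to monitor symptoms and spread of the disease among household members. Follow-up that stops early for contacts who look uninfected removes part of the record that serves this purpose. It also removes the later samples of the group most likely to have stayed uninfected. Data and samples that were never collected cannot be recovered by any analysis. For time to conversion, the end of observation would depend on two markers of infection, serology and symptoms, rather than on the calendar or on loss of contact.

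**Working it through.** The protocol gives no figure to reproduce here. The check sets the rules side by side.

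**Step 1. Who is caught by both rules?**

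| Contact | Section 8 | Synopsis, 7.3, Annex 5 | Conflict |
|---|---|---|---|
| PCR-negative, seronegative, symptom-free at one week | Out at one week | Questionnaires to day 14, samples at 6 months | Yes |
| PCR-negative, seropositive or with symptoms | Stays | Same follow-up | No |
| PCR-negative, gave no blood | No seronegative result, so the rule is not met | Questionnaires to day 14, plus any samples agreed to | No |
| PCR-positive | Out at one week only if seronegative and symptom-free | Ancillary study ends, Predi-COVID offered | Both can end participation, on different grounds |

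The third row exists because 7.3 lets contacts choose data collection only, or part of the sampling.

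**Step 2. Can the section 8 rule be applied with the scheduled data?** Only in part.

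- 7.3 schedules blood at inclusion and at 6 months, with none at one week. The serology would have to come from the inclusion sample.
- Questionnaires go to adults and to children over 10 years. Younger children have no scheduled symptom report at one week.

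**Step 3. What does a contact in the first row lose?**

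- Questionnaires: 14 − 7 = 7 days, so half of the daily reports. The Annex 5 questionnaire asks each day whether the contact has tested positive, so self-reported conversion on days 8 to 14 is lost with them.
- Samples: 7.3 has two sampling points, inclusion and 6 months. The second is lost entirely.

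**Step 4. Is a scheduled early test lost?** Not if it is done on time. The Sanitary Inspection PCR is due 5 days after the index case's test. If inclusion falls d days after that test (d ≥ 0), the section 8 exit falls at d + 7 days, which is always later than day 5. Neither the synopsis nor 7.3 schedules another test before the 6-month visit. The loss is therefore self-report on days 8 to 14 and the 6-month samples.

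**Step 5. How many contacts?** With a minimum of 100 contacts and a share p in the first row, 100 × p are affected. The protocol gives no attack rate, seropositivity rate or symptom rate, so p is unknown. The range runs from 0 to nearly 100. A large p is plausible because the synopsis describes contacts as asymptomatic at entry, but this is inference and not a stated figure.

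**The case against.** The best defence is that section 8 is left-over text. Section 7.3 says the sampling strategy was adapted to the new PCR recommendation. Section 8 also still speaks of questionnaires over 12 months, although section 2.4 extends follow-up to 2 years. The synopsis, 7.3 and Annex 5 agree with one another, so staff would probably follow them. This is a fair reading and lowers the severity. But the protocol does not say so, and section 8 is where staff would look for a discontinuation rule.

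A second defence is that a period of up to 14 days allows a shorter one. That does not meet Annex 5, which gives 14 days, and it cannot account for the 6-month visit.

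A reader might also infer more than the protocol supports:

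- **That after day 7 only seropositive or symptomatic contacts remain at risk.** Contacts who gave no blood also remain. Nothing in the protocol shows that those who stay are at higher risk of later conversion.
- **That censoring is informative because only contacts not yet converted leave.** In any time-to-event analysis only those without the event can be censored. The narrower concern is that exit depends on serology and symptoms.
- **That all late conversions go unseen because of section 8.** Even under 7.3, a conversion on days 8 to 14 would surface only through self-report or testing outside the study schedule.
- **That the share of missed conversions can be given as a percentage.** Any such figure would need an assumed transmission interval and inclusion delay, and the protocol gives neither.
- **That contacts already positive at the inclusion swab are an eligibility error.** The swab is taken at inclusion, so its result cannot be an entry criterion. How such contacts are counted is an analysis definition, which may be in a statistical analysis plan not shown, as may the censoring details and household clustering.

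**Conclusion.** The contradiction between section 8 and the synopsis, 7.3 and Annex 5 stands, both on the criterion (serology and symptoms against PCR) and on the duration (one week against 14 days and 6 months). For each contact caught by both rules, applying section 8 costs 7 of 14 questionnaire days and the whole 6-month sample set. It also ends observation for time to conversion on grounds related to infection. The effect on that analysis is an inference, because 11.4 does not define its observation window. The number of contacts affected cannot be derived.

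The severity is should-fix. Predi-COVID-H is an ancillary cohort, and time to conversion appears in neither the objectives (section 3) nor the evaluation criteria (section 4).

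**What to change.** Reconcile section 8 with the synopsis, 7.3, Annex 5 and 11.4. Which rule governs is for the sponsor to decide, but the text must state one.

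- **Simplest route.** Remove the one-week serology and symptom sentence. Contacts without a positive PCR then stay in for the 14-day questionnaires and the 6-month visit, and observation for time to conversion ends at conversion or last contact. This costs one deleted sentence in section 8 and one clarifying line in 11.4. No visit, sample or questionnaire is added, since all are already scheduled in 7.3.
- **If the one-week exit is kept.** Limit the 6-month visit, the 14-day questionnaires and the time-to-conversion analysis to the contacts who remain, and amend the synopsis, 7.3, Annex 5 and 11.4 accordingly. The text would also have to say which blood sample supplies the serology, and how the rule applies to contacts who give no blood and to children who receive no questionnaire. This costs more editing and accepts the data loss described above.
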